#### 3.4. Statistical Methods

#### 3.4.1. General Overview and Plan of Analysis

The data collected are intended primarily for clinical review and interpretation. The analysis of study data will be primarily descriptive, with emphasis on tabular and graphical displays. Descriptive statistics will be used to guide decisions as to the clinical relevance of findings. Unless otherwise stated, p-values will be determined only if they appear to be warranted from the summary statistics.

All results will be displayed in the following patient groupings:

- 1) Cohort 1 TMB-301 rollover patients;
- 2) Cohort 1 TMB-202 rollover patients in the 800mg dose group;
- 3) Cohort 1 TMB-202 rollover patients in the 2000mg dose group;
- 4) Cohort 2 patients;
- 5) Total includes all patients from 1-4.

The two patients who were formerly enrolled in the investigator-sponsored IND (compassionate use) studies will be included in listings only.

For continuous data, descriptive statistics will be presented as number of patients (n), mean, standard deviation, median, minimum and maximum. For categorical data, the frequency and percentage of patients in each category will be presented. Percentages will be based on non-missing data unless otherwise specified.

Data will be described and analyzed using the SAS System Version 9 (SAS Institute Inc., Cary, NC, SAS System). Individual patient data will be presented in patient data listings.

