6.1 Cohort 1: 800 mg Every 2 Weeks

Since there are no laboratory parameters required for entry into Cohort 1 of this study, Screening procedures and Day 0 procedures are scheduled for the same day. Patients who qualify for entry into Cohort 1 of this study who are currently receiving 800 mg ibalizumab every 2 weeks will have physical and laboratory measures performed and receive the first on-study dose of ibalizumab at Screening/Day 0 as specified in the Schedule of Events (see Table 3-1). These patients will return to the clinic on Day 14 and every 2 weeks thereafter through the remainder of participation in the study for study drug administration (800 mg) and effectiveness and safety evaluations. Patients who are discontinued or who withdraw from the study prematurely will be asked to return for an Early Withdrawal visit to have all assessments detailed in the Schedule of Events for that visit performed.

6.1.1 Screening/Day 0

Screening and Day 0 (first on-study administration of ibalizumab) are scheduled for the same day. At this visit, study information will be reviewed and discussed, and the informed consent form will be reviewed and signed by the participant. No procedures, other than a preliminary verbal assessment of eligibility by review of inclusion/exclusion criteria, may be done before the informed consent process is complete. Once informed consent has been obtained and documented, the following procedures may be completed (pre-infusion):

- Record demographics, medical history (general and HIV), and the patient's height
- Record all prior ART exposure; record all other medications taken within the last 30 days
- Record results of a complete physical examination
- Record vital sign measurements

- Record the patient's weight
- Record all AEs that begin after the patient has signed the informed consent (see [Section 8.1](#) for definitions)
- Collect blood and urine for the following laboratory samples:
 - Hepatitis serology and C-reactive protein
 - Clinical laboratory assessments (serum chemistry, hematology, and urinalysis; see [Section 7.2.2](#) for a complete list of parameters)
 - Archive sample
 - Serum pregnancy test in females of childbearing potential and a follicle-stimulating hormone (FSH) test in postmenopausal females
 - HIV-1 RNA (viral load)
 - HIV-1 viral resistance sample (will be stored for later use if needed)
 - CD4⁺ cell count (within 1 hour before the start of the infusion)
 - Immunogenicity of ibalizumab

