## 3.2. Analysis Populations

## 3.2.1. Intent-to-Treat (ITT) Population

The ITT population is defined as all patients enrolled into the TMB-311 study. The ITT Analysis Population will be used for the patient disposition, demographic and physical characteristics, and efficacy analyses.

If there are ITT patients who do not receive at least one complete dose of study drug, then a modified ITT (mITT) Analysis Population will be used for a supportive effectiveness analysis.

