## 3.2.2. Safety (SAF) Population

All patients who receive at least one partial dose of study drug will be included in the SAF Population. Patients will be analyzed according to the treatment they actually received. The SAF Population will be used for the safety analyses.

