## 4. Statistical Analysis

## 4.1. Patient Disposition

The number of patients in the ITT and SAF Populations will be tabulated.

Study completion data will be summarized for all enrolled patients. The number and percent of patients who complete treatment; discontinue study medication prematurely; or discontinue the study prematurely will be tabulated. The primary reason for premature discontinuation of study medication and/or discontinuation from study participation will be tabulated. Any additional reason(s) for premature discontinuation of study medication will also be tabulated. A listing of all enrolled patients will be provided.

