#### 4.3.2. **AEs**

All AEs will be coded, using MedDRA dictionary version 17.0. The use of another version will not be considered a violation of the SAP, nor require an amendment to the plan. All summary tables will be based on coded preferred terms (PTs), instead of verbatim terms. The only exception being all rashes are combined into one category named RASHES. The categories and definitions of severity and causal relationship for all AEs, including the criteria for which an AE is to be classified as "serious," are as described in the protocol (Section 8).

A treatment-emergent AE (TEAE) is defined as any event not present before exposure to study drug or any event already present that worsens in either intensity or frequency following exposure to study drug. AEs with missing start dates, but with stop dates either overlapping into the dosing period or missing, will be considered TEAEs. A TEAE with missing severity or relationship will be considered severe or related, respectively.

The overall incidence of TEAEs will be summarized for all patients in the SAF Population. The number and percentage of patients having the following will be tabulated:

- TEAE
- Serious TEAE
- TEAE leading to discontinuation
- TEAE with outcome of death
- TEAE related to study drug (definitely, probably, or possibly)

- Severe TEAE
- Class C TEAE per the Centers for Disease Control and Prevention (CDC) Classification System for HIV Infection

The overall incidence of TEAEs will also be summarized by System Organ Class (SOC), and by SOC and PT. The number and percentage of patients reporting an event, as well as the number of events reported by the patients will be tabulated. The incidence of serious TEAEs and TEAEs leading to study discontinuation (if any) will be summarized in the same manner. If there are multiple occurrences of the same TEAE within any SOC or PT for the same patient, only the first occurrence will be counted.

The incidence of TEAEs by severity/grade (mild, moderate, severe, or potentially life-threatening) and by relationship to study drug (unrelated, possibly related, probably related, and definitely related), and the incidence of SAEs by relationship to study drug, will also be summarized.

All other AEs will be classified as non-TEAEs and identified in listings only. Serious TEAEs, TEAEs leading to study discontinuation, and TEAEs with an outcome of death will be presented in separate listings, if needed.

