**CONFIDENTIAL** 

# **Notes Applicable to All Listings**

#### General Programming Notes:

- 1. There are a few listings that might fit as they are or might have to be split once we see the output with actual data.
- 2. All listings should start with and be sorted by Patient ID (concatenation of site number and patient number) and then visit date as appropriate.
- 3. If columns with specific text should be widened due to the amount of text, it is up to the programmer's discretion. However, please keep to the industry standard margin of 1 inch on bottom and sides and 1.25 inches on the top. Font is Courier New 8 point.
- 4. For all dates used, character format dates to capture partial dates. Use dashes where a month or day is missing. If entire date is missing just leave blank. i.e., JAN2011 or 01-2011.
- 5. If a programming note appears on the mock listing indicating that the footnote should appear only on the first page, this means the first page of output contains all footnotes and ONLY footnotes. All subsequent pages contain data with one footnote that says "Refer to page 1 for footnotes".
- 6. Some of the mock tables display numbers rather than x's. The numbers are meaningless and are for example only. Where visit names are displayed in tables, these are examples as well. Correct visit names for the TMB-311 study should be displayed in the actual output.
- 7. Each listing should include all applicable data, even if only a subset of the full set of treatment groups is displayed in the mocks. And unlike the tables and graphs, the listings should also include the 2 PI-IND rollover patients.
- 8. Sort each listing by Treatment and then Patient ID where applicable.

Listing 16.2.1.1

Patient Disposition

Treatment	Patient ID Sc	reened	ITT Population [1]	SAF Population [2]	
C1:301/800mg	311-XX-XXX	YES	YES	YES	
C1:202/800mg	311-XX-XXX	YES	YES	YES	
C1:202/2000mg	311-XX-XXX	YES	YES	YES	
C2:800mg	311-XX-XXX	YES	YE:	S YES	

Intent-to-Treat (ITT) Population consists of all patients enrolled into the study.

Programming note: Add the mITT population if analyst decides it is needed later.

Westat (Created on DDMMYYYY)
S:\TMB311\DA\SAS\L PATDISP.SAS

Safety (SAF) Population consists of patients receiving at least one partial dose of study drug.

Listing 16.2.1.2 Study Discontinuation

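### Two enrolled Cohort 1 patients are left out of every table and of Total, although the SAP says the disposition and adverse event tables cover all enrolled and all dosed patients

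*SAP*

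**What the plan says.** The population definitions carry no exception. SAP 3.2.1: "The ITT population is defined as all patients enrolled into the TMB-311 study". SAP 3.2.2: "All patients who receive at least one partial dose of study drug will be included in the SAF Population". The table descriptions follow them. SAP 4.1: "Study completion data will be summarized for all enrolled patients". SAP 4.3.2: "The overall incidence of TEAEs will be summarized for all patients in the SAF Population". Protocol 9.2.2 and 9.3 set the same populations for safety and disposition.

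SAP 3.4.1 sets the display groups for all results: TMB-301 rollovers, TMB-202 rollovers on 800 mg, TMB-202 rollovers on 2,000 mg, and Cohort 2. It then says "Total includes all patients from 1-4" and adds: "The two patients who were formerly enrolled in the investigator-sponsored IND (compassionate use) studies will be included in listings only". Note 7 of the general programming notes for the listings confirms the intent: "unlike the tables and graphs, the listings should also include the 2 PI-IND rollover patients".

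SAP 2.1 places patients from investigator-IND (compassionate use) protocols in Cohort 1. Under Protocol 6.1, Cohort 1 patients on 800 mg "receive the first on-study dose of ibalizumab at Screening/Day 0"; Protocol 6.2 provides the same for those on 2,000 mg.

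**The concern.** Both sets of instructions cannot be followed. A table of all enrolled patients, or of the whole safety population, must include these two; a table built on the four groups cannot.

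The conflict falls on the primary safety variable. The protocol synopsis makes adverse events and discontinuations primary for both cohorts, and the Cohort 1 objectives name patients treated under investigator-sponsored INDs. A reader who relies on the tables would not see a death, serious event or discontinuation in either patient. The reported ITT and safety counts would also not match their own definitions.

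The SAP text available for review gives no reason, although the SAP explains itself elsewhere: section 4.5.1 says why rollovers are left out of the primary efficacy endpoint. Section 4.5.2 goes the other way and, for completeness, widens the secondary efficacy analyses to every cohort, which the listings-only rule also contradicts.

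A lesser point concerns the same patients. For Cohort 1 patients from outside TMB-202 and TMB-301, Protocol 9.4 takes Baseline before the first ibalizumab dose ever, while SAP 3.3.3 takes the last value before the TMB-311 Day 0 dose, when the patient is already on treatment. Under the current display rule this reaches only two patients' listing rows, where change from Baseline and the CD4 toxicity flag would be measured from an on-drug value.

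**Working it through.** There is no planned power or precision figure to reproduce: enrollment is an anticipated number and no formal testing is planned. The check is a count, followed by its effect on tabulated incidences.

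**Inputs**
- Patients omitted: 2 (SAP 3.4.1).
- Anticipated N: about 100 (SAP 3.1 and protocol synopsis); about 50 (Protocol section 5). Enrollment is not capped, so N = 150 is added as an assumption.
- Both patients belong to the safety population: inferred from Day 0 dosing in Cohort 1 (Protocol 6.1 and 6.2).
- One event in an omitted patient and none elsewhere: hypothetical.

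**Step 1: denominator.** Total = N − 2; omitted share = 2/N.
- N = 100: Total 98; 2/100 = 2.0%
- N = 50: Total 48; 2/50 = 4.0%
- N = 150: Total 148; 2/150 = 1.3%

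The size of Cohort 1 is not stated. If it were 10, 20, 30 or 40 patients (assumed), two patients would be 20%, 10%, 6.7% or 5% of it.

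**Step 2: a common event.** Five events among the tabulated patients at N = 100 give 5/98 = 5.10%. On the full population the figure is 5/100 = 5.00% if neither omitted patient had the event, and 7/100 = 7.00% if both did.

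**Step 3: a rare event.** Exact (Clopper-Pearson) 95% limits:
- for 0/n, upper limit = 1 − 0.025^(1/n);
- for 1/n, lower limit = 1 − 0.975^(1/n), and upper limit = the 97.5% quantile of Beta(2, n − 1).

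For example, 1 − 0.025^(1/98) = 3.69%.

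| N | As tabulated | Full population |
|---|---|---|
| 50 | 0/48, upper limit 7.40% | 1/50 = 2.0% (0.05% to 10.65%) |
| 100 | 0/98, upper limit 3.69% | 1/100 = 1.0% (0.03% to 5.45%) |
| 150 | 0/148, upper limit 2.46% | 1/150 = 0.7% (0.02% to 3.66%) |

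If both patients had the event at N = 100, the full figure would be 2/100 = 2.0% (0.24% to 7.04%), and the table would still show zero.

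**The case against.** The exclusion is specified in advance and stated openly, with the number and origin of the patients, and it can be read as a specific exception to general wording. No data are lost. SAP 4.1 plans a listing of all enrolled patients, and SAP 4.3.2 plans separate listings, if needed, of serious, fatal and discontinuation-related TEAEs. Note 7 puts both patients in the listings. The numerical effect is small, the rare-event case is hypothetical, and its intervals overlap heavily. The 4.0% share rests on the protocol's figure of 50, whereas the SAP says 100. The Cohort 2 primary efficacy endpoint is untouched. The table shells were not available, so a footnote there might disclose the exclusion. Pre-study data for these patients may not be held, and a column of two says little. A footnote or a named analysis set would remove the inconsistency.

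Much of this stands and limits the size of the point. It does not remove it. Disclosure in 3.4.1 does not change what 3.2, 4.1 and 4.3.2 promise, and the SAP itself places its emphasis on tables and graphs. Missing pre-study values could justify gaps in Baseline-dependent summaries, but disposition and on-study adverse events need no such values. Any difficulty in dating treatment emergence from earlier exposure applies equally to the TMB-202 and TMB-301 rollovers, who are tabulated. A footnote would correct the label but would still leave enrolled, dosed patients out of the safety incidences.

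**Conclusion.** The concern holds. The SAP's display rule contradicts its own population definitions and table descriptions, so disposition and TEAE tables would cover N − 2 patients while claiming to cover all. At the anticipated 100 patients, 2.0% of the denominator is missing. The effect on common events is negligible; the effect on a rare serious event, death or discontinuation could be the difference between zero and a non-zero count.

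This rests on both patients having been dosed on study, which is inferred from the Cohort 1 schedule, and on the SAP text available. It should be corrected, but it does not threaten the primary efficacy result. The Baseline conflict is real but separate, and adds little to the weight of the point.

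**What to change.** In SAP 3.4.1, count the two patients in Total, or add a Cohort 1 investigator-IND column that feeds Total, for the disposition, demographic, adverse event and on-study exposure tables. Apply the TEAE rule already used for the other rollovers. For items that need earlier data (Baseline weight, exposure from the first-ever dose, change from Baseline), include the patients where the data are held and footnote where they are not. Amend listing note 7 to match.

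Separately, align SAP 3.3.3 with Protocol 9.4 for Cohort 1 patients from outside TMB-202 and TMB-301, and mark listing rows where no value before ibalizumab is available.

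If the sponsor has a reason to keep them out, the minimum is to name that analysis set, give the reason, footnote every affected table, and report these patients' deaths, serious events and discontinuations in the text. That cures the label, not the omission.

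The cost is SAP wording and one column or a redefined Total. The on-study data are already collected for the listings. Some Baseline entries may stay missing, because the Cohort 1 Day 0 procedures do not list collecting values from before ibalizumab.

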## 3.4.2. Hypothesis Testing

This study is designed to evaluate the safety and efficacy of ibalizumab in treatment-experienced patients infected with multi-drug resistant HIV-1. No formal statistical hypothesis testing is planned for the study. [Note: Hypothesis testing may be performed as additional/exploratory analyses (see Section 4.6)].

## 4. Statistical Analysis

## 4.1. Patient Disposition

The number of patients in the ITT and SAF Populations will be tabulated.

Study completion data will be summarized for all enrolled patients. The number and percent of patients who complete treatment; discontinue study medication prematurely; or discontinue the study prematurely will be tabulated. The primary reason for premature discontinuation of study medication and/or discontinuation from study participation will be tabulated. Any additional reason(s) for premature discontinuation of study medication will also be tabulated. A listing of all enrolled patients will be provided.

#### 4.2. Demographic and Physical Characteristics

Summary statistics will be presented for demographic and other Baseline characteristics for the ITT Population. Tabulations for age, sex, ethnicity (Hispanic/Latino, Neither Hispanic nor Latino, Unknown), and race (American Indian/Alaska Native, Asian, Black/African American, Native Hawaiian/Other Pacific Islander, White, Unknown, or Other) will be presented. Age (years) will be calculated as the integer part of [(date of screening - date of birth + 1)/365.25]. Baseline physical characteristics, such as height (cm) and weight (kg), will also be summarized.

A listing of demographic and Baseline characteristics will be presented, as well as a listing of medical history.

## 4.3. Analysis of Safety and Tolerability

Safety and tolerability will be assessed by both clinical and laboratory examinations. Summary statistics will be presented by AEs; hematology and chemistry; vital signs, changes from Baseline, and clinically significant findings; and abnormal physical examination findings in the SAF Population. Clinical laboratory values outside the normal ranges will be flagged in patient data listings. Non-numeric data will be presented in patient data listings, but will not be tabulated.

## 4.3.1. Extent of Study Drug Exposure

Summary statistics will be presented for the cumulative dose (mg) and duration of treatment received by the patients in the SAF Population. Duration of treatment will be represented as number of days from first dose of study drug. For Cohort 1 patients, the date of their first dose of study drug in the previous study will be used. Corresponding listings will also be generated for study drug administration and OBR adherence.

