8.3 Reporting Adverse Events

The investigator is responsible for reporting to the Sponsor or designee all AEs that are observed or reported by the patient during the study (from the time the patient signs informed consent until 30 days after the last dose of study medication is given), regardless of their relationship to study drug or their clinical significance. Patients will be instructed to contact study site personnel at any time after informed consent if any symptoms develop.

To ensure compliance with FDA regulations (21 CR 312.64), site investigators must immediately report to the Sponsor all AEs that meet the SAE criteria, regardless of presumed relationship to the investigational agent. The Sponsor will carefully review the SAE information to monitor the investigational drug's toxicity profile and patient safety. If any event meets the FDA's reporting criteria, it will be submitted to the FDA as an IND Safety Report (21 CFR 312.32).

Recording of AEs will begin after study drug is first administered. Any untoward medical condition that occurs after the informed consent is signed but before the first administration of the study drug will be recorded as medical history, unless it is related to a study procedure. AEs will be recorded from the first dose of study medication and until 30 days after the last dose of study medication, regardless of its relationship to study drug. AEs will be documented in the patient's source documents and recorded in the AE section of the EDC system.

All AEs reported or observed during the study must be recorded in detail in the AE section of the EDC system and followed to a satisfactory resolution or until the Principal Investigator deems the event to be chronic or the patient to be stable.

Information to be collected includes the event term, date of onset, date of resolution, Investigator-specified assessment of severity and relationship to study drug, and seriousness, as well as any required treatment or evaluations and outcome.

Pre-existing conditions (present before the start of the AE collection period) are considered concurrent medical conditions and should NOT be recorded as AEs. However, if the pre-existing condition worsens in severity, the investigator must report it as an AE.

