9.6 Exposure to Study Medication

Duration of treatment will be presented for the mITT population.

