#### 1. Introduction

This document outlines the planned statistical analyses for data collected within the scope of the TaiMed ibalizumab protocol TMB-311, entitled "A Phase 3, Multicenter, Expanded Access Study of Ibalizumab Plus an Optimized Background Regimen (OBR) in Treatment-Experienced Patients Infected With Multi-Drug Resistant (MDR) HIV-1". This statistical analysis plan (SAP) applies to the most recent version of the study protocol (dated 11 December 2017) and will be updated as necessary if future protocol amendments warrant an update to the manner of analysis. This document was prepared in accordance with the International Conference on Harmonisation (ICH) Guideline E3: Structure and Content of Clinical Study Reports [1].

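### Cohort 1 treatment duration starts in an earlier study while the AE tables appear to cover TMB-311 only, so exposure and events are shown over different periods

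*SAP*

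**What the plan says.** SAP 4.3.1 plans two exposure measures: "Summary statistics will be presented for the cumulative dose (mg) and duration of treatment received by the patients in the SAF Population". It then defines the second: "Duration of treatment will be represented as number of days from first dose of study drug". No end date is given. For rollovers the start is moved back: "For Cohort 1 patients, the date of their first dose of study drug in the previous study will be used". No corresponding rule is written for cumulative dose. Protocol 9.6 mentions no earlier-study start and names a different population: "Duration of treatment will be presented for the mITT population".

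For adverse events, protocol 8.3 says: "AEs will be recorded from the first dose of study medication and until 30 days after the last dose of study medication". SAP 4.3.2 defines a treatment-emergent event as "any event not present before exposure to study drug or any event already present that worsens in either intensity or frequency", judged against exposure to study drug, without saying whether that exposure begins in TMB-311 or earlier for Cohort 1.

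SAP 3.4.1 displays results for three Cohort 1 rollover groups, for Cohort 2, and for a Total that pools all four. The two former investigator-IND patients appear in listings only.

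**The concern.** Safety and tolerability are a primary objective for both cohorts, and the trial is uncontrolled and descriptive. With no comparator, a reader judges whether the AE counts are high or low mainly from the exposure table. If that table includes months of treatment during which TMB-311 was not collecting events, the counts look small for the time shown.

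The Total column has a further problem. It would combine Cohort 1 time since an earlier study with Cohort 2 time since TMB-311 Day 0, so it describes no single observation period. If cumulative dose is restricted to TMB-311 and duration is not, the two exposure rows also disagree with each other.

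**Working it through.** The documents give no exposure total or AE rate, so there is no planned figure to reproduce. The check has two parts: which period the AE tables cover, and how far duration exceeds it.

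**Period of the AE tables**

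- SAP section 1 limits the plan to "data collected within the scope of the TaiMed ibalizumab protocol TMB-311".
- Protocol 6.1.1 and 6.2.1 have Cohort 1 sites record events that start after TMB-311 consent.
- Protocol 8.3 adds: "Pre-existing conditions (present before the start of the AE collection period) are considered concurrent medical conditions and should NOT be recorded as AEs". Such a condition becomes reportable only if it worsens.
- No section in the available text brings TMB-202 or TMB-301 events into the TMB-311 tables.

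Together these point to TMB-311 events only. SAP 4.3.2 does not say so for Cohort 1, so this is an inference.

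**Prior time for a TMB-301 rollover**

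Protocol 1.2 puts the first ibalizumab dose of TMB-301 on Day 7 and the end of study at Week 25. Prior time P = 25 × 7 − 7 = 168 days = 24 weeks. As a cross-check, the CD4+ listing footnote in SAP section 6 gives Week 174 for TMB-301 rollovers against Week 150 for other patients: 174 − 150 = 24. I assume no gap between the two studies.

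**Reported duration against on-study treatment time**

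With T on-study weeks, reported duration is P + T and the ratio is (P + T)/T. If a reader divided events by reported duration, the resulting crude rate would be multiplied by T/(P + T).

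| On-study weeks T | Reported weeks P + T | Ratio | Factor on a reader's crude rate |
|---|---|---|---|
| 24 | 48 | 2.00 | 0.500 |
| 48 | 72 | 1.50 | 0.667 |
| 96 | 120 | 1.25 | 0.800 |
| 144 | 168 | 1.17 | 0.857 |

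AE collection runs 30 days past the last dose. Measured against that slightly longer window, the ratios are 336/(168 + 30) = 1.70 at 24 weeks, 504/(336 + 30) = 1.38 at 48 and 1,176/(1,008 + 30) = 1.13 at 144.

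**TMB-202 rollovers**

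Their prior time is not in the documents. As an assumed range at T = 144, the excess P/T is 48/144 = 33%, 96/144 = 67% or 200/144 = 139%.

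**Dose against duration**

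- Every-2-week infusions from Day 0 to Week 144 number 144/2 + 1 = 73, so a completing TMB-301 rollover is scheduled for 73 × 800 = 58,400 mg.
- TMB-311 dose over TMB-311 time: 58,400/144 = 406 mg/week.
- TMB-311 dose over time since TMB-301: 58,400/168 = 348 mg/week.
- The TMB-301 schedule in protocol 1.2 adds 2,000 + 11 × 800 = 10,800 mg. With both measures since TMB-301: (58,400 + 10,800)/168 = 412 mg/week.

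The middle figure arises only because dose and duration cover different periods. The SAP wording permits it.

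**The case against.** The strongest objection is that the mismatch is not proven. SAP 4.3.2 and protocol 8.3 speak only of study drug or study medication, and SAP 4.3.1 uses the same term for the earlier-study infusion. The SAP also carries earlier-study information forward elsewhere: rollover Baseline comes from TMB-202 or TMB-301, and a listing footnote uses a week count 24 weeks longer for TMB-301 rollovers. Parts of the SAP section 6 shells are absent from the available text, and a footnote there might settle the matter. This stands as a limit: TMB-311-only events is much the likelier reading, but it is not stated.

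Importing earlier events would not fully align the two periods. Cohort 1 entry requires that the patient is already on ibalizumab, so the prior time of these patients cannot contain a death or a permanent stop. Discontinuations are a named primary safety variable.

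Two further objections stand. Time since first ibalizumab dose is a legitimate long-term exposure measure, openly stated in the SAP. AEs are summarised as patient counts, percentages and event counts, so no planned statistic is numerically wrong.

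The separate group columns confine the mixing of clocks to Total, and Cohort 2 is unaffected. The study drug administration listing lets on-study exposure be recovered patient by patient, but not from the summary table.

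**Conclusion.** The point holds as a mismatch of reference periods, and it is worth correcting. For TMB-301 rollovers, reported duration exceeds on-study treatment time by 17% for a 144-week completer, 50% with 48 on-study weeks and 100% with 24. Which of these is typical is unknown, because the documents give no distribution of on-study time. The figures assume continuous transfer from TMB-301. The TMB-202 range of 33% to 139% at 144 weeks rests wholly on assumed prior times.

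A reader might infer that the plan will report Cohort 1 AE rates that are too low, for example by one third at 48 weeks, or that the added time is free of events. The documents support neither. No person-time rate is planned, so that reduction applies only to a rate a reader might construct. Protocol 1.2 reports AEs in the earlier studies; they appear simply not to be counted here. Nor can it be said that the factor is larger for TMB-202 rollovers, since their prior time is not stated.

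**What to change.** In SAP 4.3.1, summarise TMB-311 exposure for every display group and for Total: duration from first to last TMB-311 dose, with cumulative mg over the same period. This is the summary to read beside the AE tables, and it also supplies the missing end date. Keep time since first ever ibalizumab dose as a separate, labelled row for Cohort 1. In SAP 4.3.2, state that Cohort 1 TEAEs are counted over the same TMB-311 period. In the same edit, reconcile the exposure population (SAF in the SAP, mITT in protocol 9.6).

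The cost is one extra table row and a few sentences. Infusion dates and doses are already planned for Listing 16.2.5.1, so no new data are needed and the long-term exposure figure is kept.
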